## 5.2 Recruitment Methods

### **Aim 1: Formative Interviews and Design Team Meetings:**

**Participants:** There are two groups of participants for aim 1

- **Healthcare providers (both ID and primary care). up to 18 health care providers** (n=6 providers from each site, a mix of provider type (MD, RN, NP, PA, PharmD) will participate. Providers will be recruited by purposive and snowball sampling. We will first interview providers to seek their guidance on key factors on which to select our Veteran informants.
- **Veterans with HIV: up to 18 Veterans** (n=6 from each site) will participate. They will be enrolled by purposive sampling.

We will use nonprobability sampling techniques of purposive and snowball to recruit participants for this aim.

A purposive sampling strategy is a “judgmental or expert sample” and is a type of nonprobability sample. The objective of purposive sample is to produce a sample that can be logically assumed to be representative of the population. This is often accomplished by applying expert knowledge of the population to select, in a nonrandom manner, a sample of elements that represents a cross-section of the population. To achieve representative, yet nonrandom sample of patients for our qualitative interviews, we will first query the context experts on the study team and at the site level to ascertain key variables (eg., age, race/ethnicity, sex, comorbidities) upon which to sample the eligible population of patients with HIV and CVD risk. Based on these typologies, we will query CDW based on these variables and then develop a purposive sample based on these characteristics. In some instances, we will also use direct nominations by site leaders and providers, when feasible.

We will then mail introductory letters to Veterans who meet these criteria using a strategy whereby Veterans may call a toll-free number to opt out. The letters are on VAMC letterhead and signed by the study site PIs (attached). If patients meet telephone screening criteria and are interested in participating, we will complete the informed consent process by telephone before scheduling the qualitative interviews.

For providers, we will predominantly use a snowball sampling (ie., chain sampling, chain-referral sampling) which is another a nonprobability sampling technique. In snowball sampling, existing study participants help identify future participants from among their social network such that the sample group is said to grow like a rolling snowball. For this protocol, we will work with site leads to identify a beginning set of site providers. We will then ask these providers to nominate others they see as important to the implementation of the intervention while balancing mix of providers (eg. MD vs NP). In order to protect the identity of providers who are contacted, we will create a firewall between the study and management – that is, there will be no record for which management can be aware of which providers were contacted nor which providers agreed to participate. We will contact providers by encrypted email, with introductory information about the study (attached). Research staff will reach out to providers after the emails are sent to assess interest in participation, and will conduct the

informed consent process by phone before scheduling any interviews. Participation with providers can be done by all authorized communication methods approved by VA, such as email, Microsoft Teams, phone call.

For Aim 1b (design meetings), we plan to consent approximately 10-20 design team members across the 3 VA sites: a mix of healthcare providers, and Veterans with HIV. These healthcare providers and Veterans will most likely be those who already participated in the Aim 1a qualitative interviews and expressed interest in the design meetings, but they will undergo another verbal consent process with specific details to the design meeting process.

See table below regarding payment to Veterans for participation in the project. Providers/staff will not be compensated.

### **Aim 2: Evaluate the 12-month efficacy of interventionist intervention**

**Participants:** We plan to enroll 300 HIV+ Veterans who are on suppressive ART with **HIV-1 RNA <200 copies/ml** checked at least twice within the prior year if they have hypertension and receive care at the 4 clinic sites. Our plan is to enroll approximately 100 from each of the following sites the Durham VA Healthcare System, Cleveland VA Healthcare system, Baltimore VA HealthCare System and the Atlanta VA Healthcare System. We may enroll more or less at the different sites depending on acceptance of study at the sites. Since site is one of our randomization strata enrolling more at one site will not impact analysis. Additionally, while 300 is our enrollment goal, we may consent and randomize up to 310, to account for site differences, withdrawals and the scheduling availability and preferences of Veteran participants.

The study programmer and statistician in Durham will use VA Corporate Data Warehouse to identify a sample population at each facility for Veterans enrolled in care at through either primary care clinics or infectious disease clinics. ICD-10 diagnostic and procedure codes will be used to identify patients meeting the inclusion/exclusion criteria. Research assistants will use each site's respective electronic medical record system (CPRS) for a second screening level for information not readily available as normalized data in VA CDW prior to mailing letters. Research assistants will also be able to conduct chart reviews, to assess eligibility, for other study sites using Joint Longitudinal Viewer (JLV).

The primary outcome is change in systolic BP and the secondary outcome will be change in non-HDL cholesterol. Separately for hypertension and hypercholesterolemia, we will then examine changes in the three extended treatment cascade categories (1) % appropriately diagnosed, (2) % appropriately managed, and (3) % at treatment goal. We chose BP as the primary outcome because the V-EXTRA-CVD intervention components were designed primarily to address BP management, with cholesterol management being an important but secondary consideration. For the purposes of determining cascade level #1, we will use the following table to search for diagnosis of high cholesterol or blood pressure in the medical record.

**Table:** Diagnosis terms for high cholesterol and high blood pressure for the purposes of determining cascade category from chart review.

High Cholesterol	High Blood Pressure
Hyperlipidemia	Hypertension
Dyslipidemia	Essential Hypertension
Hypertriglyceridemia	Secondary Hypertension
Hypercholesterolemia	Hypertensive end-organ disease
Elevated LDL	High blood pressure
Elevated Triglycerides	
Elevated Cholesterol	
Familial Hypercholesterolemia	

DO NOT include the following:	DO NOT include the following:
Low HDL	Pulmonary hypertension
	Intracranial hypertension
	Venous hypertension
	Pre-eclampsia or Maternal Hypertension
	Portal hypertension
	Ocular hypertension

Specific recruitment strategies may vary at each site depending on the preferences of the clinic providers and Veteran populations, but will include a mix of the following methods:

1. The research team will mail introductory letters to Veterans who meet eligibility criteria using a strategy whereby Veterans may call to opt out. The letters are on VAMC letterhead and signed by the study site PIs.
2. Medical providers in their clinics may talk to their patients about the study and refer potentially eligible and interested patients to the site's research assistant.
3. Study-specific flyers and brochures will be made available at each of the site's clinics, allowing Veterans to self-select and call the research team for more information.

The research assistant will contact potentially eligible Veterans and administer a screening questionnaire to further assess eligibility. This may be done by phone, or in-person (if a patient is already on-site for an appointment and able to meet with the research team). If patients meet screening criteria and are interested in participating, we will schedule an enrollment visit to coincide with an upcoming clinic appointment or the availability of the Veteran. If  $\geq 30$  days pass between initial chart review and date of consent, chart review may be repeated to confirm eligibility at time of consent.

All enrolled participants will complete a baseline assessment which includes in-office BPs, lipid panels, and several health-related surveys (see section 5.5 study evaluations). On return visits at 4, 8 and 12 months all participants will similar assessments. Participants will be randomized during the baseline visit.

Participants in both study arms will be paid a total of \$150: \$50 for completion of the baseline questionnaires at the enrollment visit and \$50 for completion of the 12-month blood pressure and lab outcome assessment and questionnaires. They will be paid \$25 for completion of the 4 & 8 month blood pressure and lab outcome assessment. These are the only study sessions that require in-person visits. If due to unforeseen reasons or closures, we are unable to obtain BP by study personnel, we may conduct VVC visit with study participant to observe the collection of self-monitored BP and schedule patient for lab collection within next 4 weeks. The research assistant completing the assessments will submit the payment voucher following each visit after we receive the results of labs.

### **Aim 3: Process Evaluation**

**Participants:** A random subset of approximately n=27-40 intervention participants (4-16 from each site) will complete key informant interviews at the conclusion of the intervention. Participation in these interviews will be voluntary and discussed when they provide informed consent to the intervention (aim 2). Selection of VA providers will be based on those currently employed in ID or Primary Care clinics at the 4 study sites, and those who interacted with the study team during the intervention (most likely ID physicians whose patients enrolled in the study, and were responsible for making changes to medications after health coach recommendations). Veterans will be paid \$20 for completion of interview. Providers/staff will not be compensated.

### **Exploratory Aim: Cost Evaluation**

**Participants:** If effective, we will conduct a budget impact analysis and simulate 10-year cost-effectiveness of the interventionist intervention. The entire cohort of Aim 2 will be used in the budget impact analysis and the intervention cohort will be used in the 10 year cost effective analysis.

## **Participant payments:**

The research assistant completing the assessments will submit the payment voucher following each visit. Providers/staff will not be compensated.

Aim 1 – Formative evaluation & adaptation	Formative interview (n=18) Design Meetings to adapt intervention (n=6) Phone interview to review acceptability of intervention revisions (n=12)	\$20 \$120 per meeting (\$480 total) \$20
Aim 2 – Interventionist-led intervention	In-person study outcome assessments (n=300)  Months 0, 12  Months 4, 8	\$50 each \$25 each
Aim 3 – Process evaluation	Post-intervention qualitative interview (n=27-40), as well as 6-12 month post-intervention sustainability interview	\$20 each

## **5.3 Informed Consent Procedures**

Subjects for each aim will go through the informed consent process to participate in the study. Research staff (RA or PC) will read, review, and discuss consent documents with all potential participants prior to obtaining consent. If the veteran appears confused or indicates a lack of understanding, the interviewer will attempt to identify the misunderstanding and to explain the study again. Any veteran who still does not comprehend the consent process and study will be excluded from the study. Veterans who understand the consent process and study and agree to participate in the study will be asked to provide consent either verbal or written. For those participants who provide written informed consent, the research assistant will keep the original signed and dated consent documents and will provide a copy of the signed documents to the subject. No veterans who have impaired decision-making abilities will be enrolled in any phase of the study. These consent procedures will take place in a private room or office. Written consent and HIPAA forms will be kept in a locked file cabinet within a secure office at each of the 3 sites. Verbal consent will be documented in RedCap & tracking database.

Aim 1: Formative Evaluation/Qualitative Interviews and Design Team Meetings. These interviews and meetings will be done by telephone, with no in-person contact, therefore we will request a waiver of documentation of informed consent as well as waiver of HIPAA. Research staff (RA, PC, or investigator conducting the interviews) will collect verbal informed consent from both the veteran and provider participants for Aim 1. Date of verbal consent obtained will be documented in tracking database or REDCap along with the name of the person who obtained consent.

Aim 2: Intervention. Once the veteran is screened and agrees to enroll, then written informed consent and HIPAA authorization will be obtained at the baseline visit. These visits will be handled by the research assistant at each of the 3 sites. The project coordinator is also trained and able to assist with these visits. All research staff (RAs and PCs) will be up to date on all CITI training and how to obtain and document informed consent.

Aim 3: Process Evaluation: Participation in this aim will be a voluntary addition when providing informed consent for the intervention (aim 2). It will be covered by the same written consent and HIPAA authorization as Aim 2. For clinicians contacted for their feedback, language will be provided (by VA encrypted email or verbally on Microsoft Teams/telephone) related to providing consent

All study personnel will maintain certification of completed training in research ethics and confidentiality, data privacy and security. The study/site PIs will meet with research staff before the study begins to review eligibility and study procedures including obtaining informed consent and documentation of informed consent and authorization. If required by local site IRB/R&D/RCO, the research assistant will enter the research consent note into CPRS within 24 hours of the subject signing the consent and attach the scanned informed consent, HIPAA authorization as soon as possible but no later than 14 days from the signed consent.

## 5.4 Inclusion/Exclusion Criteria

The same inclusion and exclusion criteria is used for Veterans enrolled in all aims.

	Inclusion Criteria	Exclusion Criteria
Veterans with HIV Aim 1: N= 18 Aim 2: N= 300 Aim 3: N = 27	
 
1. Age <math>\geq</math> 18 years
 
2. Confirmed HIV+ diagnosis
 
3. Undetectable HIV viral load: defined as the most recent HIV viral load <math>< 200</math> copies/mL, checked within the past 18 months (assessed via chart abstraction)
 
4. Hypertension: defined as having 2 recent outpatient BP measurements in the last 18 months to show systolic BP <math>\geq 130</math> and/or diastolic <math>\geq 90</math> mmHg OR being prescribed anti-hypertensive medication (assessed via chart abstraction)
 
5. Veteran at one of the sites participating in the study
 
	
 
1. Severely hearing or speech impaired, or other disability that would limit participation
 
2. In a nursing home at baseline and/or any long-term care facility. Individuals will be censored at the point of entering nursing home care
 
3. In-patient psychiatric care
 
4. Diagnosis of dementia or active psychosis
 
5. Terminal illness with life expectancy <math>< 4</math> months (ex. Metastatic cancer, Hospice care,)
 
6. Recent (<math>< 90</math> day) hospitalization for CABG, MI, stroke)
 
7. Pregnant, breast-feeding, or planning a pregnancy during the study period
 
8. Planning to move out of the area in the next 12 months.
 
9. No reliable access to telephone services
 
10. Currently enrolled in a competing research study (e.g. an intervention that may impact BP management)
 

Providers (infectious disease and primary care) Aim 1: N= 18 (2 HIV MDs, 2 PCPs, 2 RNs per site) Aim 3: N = 6	
 
1. Have a panel of at least 10 veterans with HIV.
 
	
 
1. Not a provider at one the 3 participating facilities
 
2. PI is a co-investigator on the study.
 

**Table: Antihypertensive Medications –**

Beta Blockers	CARVEDILOL ESMOLOL METOPROLOL TIMOLOL BISOPROLOL NADOLOL ACEBUTOLOL	ATENOLOL BETAXOLOL LABETALOL PINDOLOL PROPRANOLOL NEBIVOLOL PENBUTOLOL SOTALOL
Alpha Blockers	SILODOSIN TAMSULOSIN TERAZOSIN	DOXAZOSIN ALFUZOSIN PRAZOSIN
Calcium Channel Blockers	AMLODIPINE NICARDIPINE AMLODIPINE/CELECOXIB CLEVIDIPINE ISRADIPINE NISOLDIPINE	AMLODIPINE/ATORVASTATIN DILTIAZEM NIFEDIPINE VERAPAMIL FELODIPINE NIMODIPINE
Antihypertensi ve Combinations	ALISKIREN/HYDROCHLOROTHIAZIDE AMLODIPINE/PERINDOPRIL ATENOLOL/CHLORTHALIDONE CANDESARTAN/HYDROCHLOROTHIAZIDE CAPTOPRIL/HYDROCHLOROTHIAZIDE HYDROCHLOROTHIAZIDE/IRBESARTAN HYDROCHLOROTHIAZIDE/LOSARTAN HYDROCHLOROTHIAZIDE/METHYLDOPA HYDROCHLOROTHIAZIDE/PROPRANOLOL AMLODIPINE/BENAZEPRIL BENDROFLUMETHIAZIDE/NADOLOL EPROSARTAN/HYDROCHLOROTHIAZIDE FOSINOPRIL/HYDROCHLOROTHIAZIDE HYDROCHLOROTHIAZIDE/LISINOPRIL HYDROCHLOROTHIAZIDE/METOPROLOL HYDROCHLOROTHIAZIDE/MOEXIPRIL HYDROCHLOROTHIAZIDE/TELMISARTAN	TRANDOLAPRIL/VERAPAMIL AMLODIPINE/OLMESARTAN AMLODIPINE/VALSARTAN AZILSARTAN/CHLORTHALIDONE BENAZEPRIL/HYDROCHLOROTHIAZIDE BISOPROLOL/HYDROCHLOROTHIAZIDE ENALAPRIL/HYDROCHLOROTHIAZIDE HYDRALAZINE/ISOSORBIDE SACUBITRIL/VALSARTAN AMLODIPINE/HYDROCHLOROTHIAZIDE/OLMES ARTAN AMLODIPINE/HYDROCHLOROTHIAZIDE/VALSAR TAN AMLODIPINE/TELMISARTAN HYDROCHLOROTHIAZIDE/OLMESARTAN HYDROCHLOROTHIAZIDE/QUINAPRIL HYDROCHLOROTHIAZIDE/VALSARTAN
Antihypertensi ves, other	CLONIDINE METHYLDOPATE RIOCGUAT TADALAFIL GUANABENZ GUANFACINE MECAMYLAMINE	LOFEXIDINE MACITENTAN METHYLDOPA METYROSINE HYDRALAZINE ILOPROST SILDENAFIL

	MINOXIDIL	SODIUM NITROPRUSSIDE
Peripheral Vasodilators	ISOXSUPRINE PAPAVERINE	
Thiazides / Related Diuretics	HYDROCHLOROTHIAZIDE CHLOROTHIAZIDE CHLORTHALIDONE	INDAPAMIDE METOLAZONE
Loop Diuretics	FUROSEMIDE ETHACRYNIC ACID TORSEMIDE BUMETANIDE	
Carbonic Anhydrase Inhibitor Diuretics	DICHLORPHENAMIDE METHAZOLAMIDE ACETAZOLAMIDE	
Potassium Sparing / Combination Diuretics	HYDROCHLOROTHIAZIDE/SPIRONOLACTONE HYDROCHLOROTHIAZIDE/TRIAMTERENE AMILORIDE	AMILORIDE/HYDROCHLOROTHIAZIDE EPLERENONE SPIRONOLACTONE TRIAMTERENE
Diuretics, other	CAFFEINE/MAGNESIUM SALICYLATE MANNITOL SPIRONOLACTONE PAMABROM	
ACE Inhibitors	BENAZEPRIL CAPTOPRIL ENALAPRIL FOSINOPRIL QUINAPRIL	LISINOPRIL MOEXIPRIL RAMIPRIL ENALAPRILAT TRANDOLAPRIL PERINDOPRIL
Angiotensin II Receptor Antagonists	AZILSARTAN CANDESARTAN EPROSARTAN IRBESARTAN	LOSARTAN OLMESARTAN TELMISARTAN VALSARTAN

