We plan to enroll 300 HIV+ Veterans who are on suppressive ART with **HIV-1 RNA <200 copies/ml** checked at least twice within the prior year if they have hypertension and receive care at the 4 clinic sites. Our plan is to enroll approximately 100 from each of the following sites the Durham VA Healthcare System, Cleveland VA Healthcare system, Baltimore VA HealthCare System and the Atlanta VA Healthcare System. We may enroll more or less at the different sites depending on acceptance of study at the sites. Since site is one of our randomization strata enrolling more at one site will not impact analysis. Additionally, while 300 is our enrollment goal, we may consent and randomize up to 310, to account for site differences, withdrawals and the scheduling availability and preferences of Veteran participants.

Inclusion Criteria:

Variable	Description	Variables and Source	Specifications
1. Age \geq 18 years 2. Confirmed HIV+ diagnosis 3. Undetectable HIV viral load: defined as the most recent HIV viral load < 200 copies/mL, checked within the past 18 months (assessed via chart abstraction) 4. Hypertension: defined as having 2 recent outpatient BP measurements in the last 18 months to show systolic BP ≥ 130 and/or diastolic ≥ 90 mmHg OR being prescribed anti-hypertensive medication (assessed via chart abstraction) 5. Veteran at one of the sites participating in the study sites			

Some of these are specific to clinical trials (based on this [JAMA paper](#)) and some are other are specific to observational studies (based on [STROBE/RECORD](#) guidelines),

Statistical Analysis Plan

Project: A nurse-led intervention to extend the Veteran HIV treatment cascade for cardiovascular disease prevention (V-EXTRA-CVD)

Principal Investigators: [name] PhD

Deliverable (e.g., manuscript, report): Manuscript

Exclusion Criteria:

Variable	Description	Variables and Source	Specifications

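### Eligibility criterion 4 accepts a prescription alone as hypertension, and the protocol's drug list includes entries generally used for other conditions, so veterans without systemic hypertension could qualify

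*Protocol*

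**What the plan says.** Criterion 4 (Protocol 5.4; SAP, Study Population, Inclusion Criteria) can be met in two ways. One is two outpatient readings in the last 18 months with systolic pressure of at least 130 and/or diastolic of at least 90 mmHg. The other is "OR being prescribed anti-hypertensive medication (assessed via chart abstraction"). The second route asks for no reading, diagnosis or indication.

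Directly under the criteria, Protocol 5.4 gives "Table: Antihypertensive Medications", the only such list in either document. No sentence in the protocol or SAP refers to it. Among its rows are:

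- alpha blockers: "SILODOSIN TAMSULOSIN TERAZOSIN" and "DOXAZOSIN ALFUZOSIN PRAZOSIN"
- other antihypertensives: "CLONIDINE METHYLDOPATE RIOCGUAT TADALAFIL GUANABENZ GUANFACINE MECAMYLAMINE" (riociguat is misspelled) and "LOFEXIDINE MACITENTAN METHYLDOPA METYROSINE HYDRALAZINE ILOPROST SILDENAFIL"
- other diuretics: "CAFFEINE/MAGNESIUM SALICYLATE MANNITOL SPIRONOLACTONE PAMABROM"
- carbonic anhydrase inhibitors: acetazolamide, methazolamide and dichlorphenamide

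No footnote limits an entry by indication.

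Three other places bear on this. The Specific Aims (Methodology), Protocol 3.0 and the SAP's Study Design describe participants with systolic pressure confirmed above 140 mmHg. The diagnosis-terms table in Protocol 5.2 lists "Pulmonary hypertension", and also ocular hypertension, among the terms not to count as high blood pressure. The power paragraph in Protocol 5.6 assumes a mean baseline SBP of 145 mmHg.

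**The concern.** Several listed drugs are generally prescribed for something other than systemic hypertension: tamsulosin, silodosin and alfuzosin for the prostate; sildenafil and tadalafil for erectile dysfunction or pulmonary hypertension; macitentan, riociguat and iloprost for pulmonary hypertension; acetazolamide and methazolamide for eye pressure; pamabrom as a mild diuretic. If the list is what chart abstractors use for criterion 4, a normotensive veteran taking one of these meets the hypertension criterion, and none of the ten exclusions removes him.

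Two things are at stake. The first is dilution: under Protocol 5.1 the medication component is for participants not at goal, and medication review is triggered by average readings above 140/90 mmHg, so much of the intervention would have little to act on in such a participant. The second is description: a report of a trial in veterans with poorly controlled hypertension would include some who have no hypertension.

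**Working it through.** **1. Does any written rule stop such an entry?** Criterion 4 joins its two routes with OR. The recruitment text in Protocol 5.2 refers to enrolling veterans if they have hypertension, but criterion 4 is what defines hypertension, so that wording adds no test. ICD-10 codes are used in screening, but no criterion requires a hypertension code. The SBP >140 description is not among the inclusion criteria. The answer on the text is no.

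**2. Reproducing the plan's power.** Inputs (Protocol 5.6, Power): SD 17; within-person correlation 0.4; missing 5%, 10% and 15% at 4, 8 and 12 months; two-sided alpha 0.05; N = 300, 1:1; effect 6 mmHg. Model: common intercept, three visit terms, three arm-by-visit terms, compound symmetry. I took the missingness as monotone drop-out: 85% with all four visits, then 5% each leaving after 8 months, after 4 months and after baseline.

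- Generalised least squares gives SE(β7) = 1.94 mmHg.
- Rough check by baseline-adjusted comparison: residual SD = 17 × √(1 − 0.4²) = 15.58; completers per arm = 150 × 0.85 = 127.5; SE = 15.58 × √(2/127.5) = 1.95.
- Power = Φ(d/SE − 1.96) = Φ(6/1.94 − 1.96) = 87.1%, consistent with the stated >80%.
- Against Table 4 at 80% power, the same method gives 355, 246 and 181 for 5, 6 and 7 mmHg; the plan has 350, 234 and 178. The gaps are plausible noise from 1,000 simulations.

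**3. Dilution.** The documents give no share, so let q be the share entering only through such drugs, r their effect, and 6 mmHg the effect in everyone else, with the SD held at 17. The overall effect is d = 6(1 − q) + rq.

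| q | d if r = 0 | Power | d if r = 3 | Power |
|---|---|---|---|---|
| 0 | 6.0 | 87.1% | 6.0 | 87.1% |
| 5% | 5.7 | 83.6% | 5.85 | 85.4% |
| 10% | 5.4 | 79.5% | 5.7 | 83.6% |
| 20% | 4.8 | 69.6% | 5.4 | 79.5% |

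The effect detectable with 80% power is (1.960 + 0.842) × 1.9405 = 5.44 mmHg. The break-even share is therefore (6 − 5.437)/6 = 9.4% when r = 0, about 28 of 300, and (6 − 5.437)/3 = 18.8% when r = 3, about 56 of 300.

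**The case against.** **The link between list and criterion is inferred.** This stands. The table could instead be a coding aid for the medication abstraction at months 0, 4, 8 and 12 (Protocol 5.5). Its title and position point to criterion 4, though, and if it is not the operational list, the prescription route has no definition at all.

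**Indications come from general pharmacology.** This also stands. The documents do not say what these drugs are for. The only internal support is the 5.2 diagnosis-terms table, which bears on the pulmonary and ocular examples. A reader might infer that this table contradicts the eligibility list outright. It does not: it is a list of diagnosis terms for assigning cascade category, not an eligibility rule. The two merely sit badly together. Some neighbouring entries are blood pressure agents in the protocol's own treatment text (terazosin, hydralazine, clonidine), so only particular entries are in question.

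**Sites would notice.** A reader might infer that sites will in fact enrol normotensive men on tamsulosin. The documents support only that they could: chart review and a screening questionnaire may stop some, although no written rule requires it.

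**Most dilution has another cause.** This stands. The prescription route also admits veterans whose pressure is well controlled on ordinary antihypertensives, and trimming the list leaves them in. The SAP's post-hoc moderation analysis by baseline SBP of at least 140 examines that broader group, but below 140 it cannot separate controlled hypertension from no hypertension.

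**Zero benefit is the adverse extreme.** This is fair. The lifestyle modules do not depend on raised pressure, hence the r = 3 column.

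**Conclusion.** The point holds as a gap in the eligibility definition: as written, veterans without systemic hypertension could qualify, and this does not match the stated population. The effect estimate is not biased, because entry precedes randomisation. What is exposed is the size of the SBP contrast and the accuracy of the population description.

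The size is unknown. A reader might infer that the >80% power claim fails. That is not shown: it would take about 9% entering this way with no benefit, or about 19% with a 3 mmHg benefit, and the true share is probably smaller because many users of these drugs also have hypertension. These thresholds assume the plan's SD, correlation and missingness, and a 6 mmHg effect in everyone else.

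A reader might also infer that the hypertension cascade results are corrupted. The documents do not support that: they define no cascade denominators, Protocol 2.0 frames the first step as diagnosing abnormal values, and the SAP plans no cascade analysis.

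**What to change.** **Eligibility text.** Reconcile criterion 4, the drug list and the SBP >140 description in Protocol 5.4 and the SAP. Either count the prescription route only with a charted hypertension diagnosis, using the 5.2 terms, or remove the entries that are not systemic antihypertensives. State in one sentence that the list defines criterion 4, if it does.

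**Participants already randomised.** Derive a flag from pre-randomisation data: entered only through a listed drug, no charted hypertension diagnosis at month 0, and no two qualifying readings. Split its count by whether the drug is one of the questioned entries, so that veterans on ordinary antihypertensives with no charted term are visible separately. Report the counts by arm in Table 1 and add a supportive analysis of the primary outcome without the flagged group. Leave the ITT primary analysis as it is.

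**Cost.** One amendment line, one derived variable and one extra analysis. Protocol 5.5 already has hypertension diagnosis and medications abstracted at month 0, and the qualifying readings come from the eligibility chart review. None of these is in the SAP's variable list, so they must be added there. The eligible pool becomes slightly smaller. The change does not remove dilution from veterans with controlled hypertension.
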